4.0 Description of methodology

4.1 Type of Study- study design

OPTIMATE is designed as a prospective, single-blinded, randomized controlled multi-centre study.

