4.2.1 Subjects Eligibility Criteria

Inclusion criteria:

- I. Age \geq 70 years (male or female).
- II. \geq 3 chronic medical conditions.
- III. \geq 5 daily medications pre-admission, all medications taken for at least 4 weeks continuously.
- IV. Can speak and understand English (in the two Irish medical centres), and Dutch or French in Ghent University Hospital (Ghent is predominantly Dutch-speaking).
- V. Can give written informed consent, or give witnessed verbal consent or have a suitable proxy who can give informed assent on the patient's behalf.
- VI. Agrees to follow-up contact post-discharge up to 180 days post-discharge.
- VII. Agrees to primary researcher contacting the GP and community pharmacist post-discharge.

Exclusion criteria

- I. Terminal illness.
- II. Severe dementia and clearly unable to understand the purpose of the trial or give consent to participation.
- III. Severe communication disorder, making informed consent impossible.
- IV. Likely to be discharged from hospital within 48 hours of arrival.
- V. ICU admission.
- VI. Primary psychiatric presenting illness.
- VII. Unavailable for post-discharge follow-up for any reason.
- VIII. Non-accidental poisoning.
- IX. Previous participation in medication optimization trials.
- X. Participation in another clinical trial.
- XI. Infectious illness requiring strict isolation (including COVID-19 infection) blocking access of the primary researcher to the patient for enrolment.
- XII. End-stage renal, liver or lung disease requiring organ replacement therapy.
- XIII. Admitted under the care of specialists in Clinical Pharmacology, Palliative Medicine, Clinical Oncology or Haematology.
- XIV. Admitted under the care of specialists in Geriatric Medicine in Ghent University Hospital.
- XV. Trial participation refusal.

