4.3 Sampling and Randomization (if applicable)

To test the main study hypothesis i.e. that the definitive intervention (DI) yields significantly better outcomes than standard pharmaceutical care (control), patients will be randomized in a 1:1:1 ratio to one of 3 trial arms: (a) standard pharmaceutical care as it contemporaneously exists in that hospital, or (b) trained physician-delivered intervention or (c) clinical pharmacist-delivered intervention. The 3-way randomization to control, Physician-DI and Pharmacist DI is fundamental to addressing the important secondary question: does physician-delivered DI offer any advantage over pharmacist-delivered DI?

The sample size is based on a known 180-day risk of medication-related readmission of approximately 20%. At a bilateral 5% significance threshold and 80% power, for detection of an 8% absolute reduction in readmissions, with a 1:1:1 randomization, each group must contain 324 patients i.e. 972 patients in total. With the expectation of up to 30% patient attrition, we aim to randomize $972/(1-0.3) = 1389$ patients.

The randomization will be designed by the trial statistician, but the code to create the resulting randomization lists will be executed by an independent statistician. The resulting lists will be integrated into the electronic data capture system in a manner such that trial staff never have access to the lists. Allocation of enrolled patients into treatment arms will then be delivered using a web-based system, such that the allocation remains concealed until a patient is unambiguously consented and enrolled onto the trial and cannot be altered in the underlying database once it is revealed. While the intervention will be known to clinical staff, the trial statistician and outcome assessors will remain blinded until the results are finalized.

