Within 72 hours of admission, patients who are potentially suitable for trial enrolment will be approached by the primary researchers (PRs) and informed about OPTIMATE in outline. If they meet inclusion criteria and do not have exclusion criteria, they will be asked to provide informed consent to trial enrolment. Recommended best practice for assessment of decision-making capacity of older patients who may be suitable for the OPTIMATE trial, involves formal assessment of capacity. Where necessary, the patient's mental capacity will be evaluated using the **OPTIMATE Decision-Making Capacity Functional Assessment** guidelines document in the OPTIMATE Manual of Operations. The patient will then be randomized to either the control arm (usual pharmaceutical care), pharmacist-delivered DI arm or physician-delivered DI arm of the trial. Randomization will proceed in a 1:1:1 ratio. The randomization process will be performed electronically using Castor EDC's block randomization algorithm. Patient enrolment will be sequential. With individual level randomization, there is the theoretical risk of control group contamination. This is where both control and intervention patients could be under the care of the same physician, thereby presenting a risk of medication advice learnings in intervention patients being applied unwittingly to control patients. However, in practice, as was seen in the pre-SENATOR observation study (Lavan et al.), variation in reported incidence of ADRs across various medical and surgical specialties in the 6 multi-national participating clinical sites was so large that meaningful cluster randomization was considered both impractical and unnecessary. Furthermore, in the SENATOR trial itself ([name] et al.), although uptake of medication optimization advice was generally poor, there was no evidence of contamination of the control population.

Randomization will be stratified by study site and by admitting service type (i.e. medical vs. surgical). The stratum-specific randomization lists will be generated electronically within Castor EDC, using a validated variable block randomization model. Once a patient has given consent and been enrolled onto the study, their data will be irreversibly added to the study database. From this point, the

primary researchers will receive randomization outcomes immediately upon activating the randomization request on the electronic Case Report Form (eCRF) within the Castor EDC.

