4.0 Study Procedures and Schedule of Events

The schedule of trial procedures for patient participants in the intervention arm of the trial are shown in Tables 1a and 1b below. To mimic the intervention for blinding purposes of the participants, both control and intervention arm patients will receive a sham intervention in the form of a modified version of the Medication Adherence Rating Scale (MARS; Thompson et al.).

Table 1a: Schedule of events for intervention patients

Timepoints	0/1	2	3	4	5
Study Visit	Baseline (within 72 hours of admission)	Pre-discharge (within 48 hours pre-discharge)	1 Week Follow-up (within 10 days post-discharge)	1 Month Follow-up (within 30 days post-discharge)	6 Month Follow-up (between 90 and 180 days post-discharge)
	Day 1	Day variable	Day 10 (+/- 3 days post-discharge)	Day 30 (+/- 7 days post-discharge)	Between Day 90 and Day 180 post-discharge
Inclusion / Exclusion criteria	X				
Decision-Making Capacity Functional Assessment	X	X**		X**	X**
Informed consent/ proxy assent	X	X**		X**	X**
Patient Demographics	X				
Medical History	X	X		X	X
Medication Reconciliation	X	X		X	X

OPTIMATE Trial

Principal Investigator: [name] [name]

FORTA* criteria	X	X		X	X
Laboratory Results	X	X			
Electrocardiogram review	X				
EQ5D-5L				X	X
Randomization	X				
Medication History (modified SHiM)	X				
Modified Medication Adherence Rating Scale (mMARS)	X				
Barthel Index Score	X	X			
Drug-drug interactions (Stockley's)	X	X		X	X
STOPP/START criteria (PIMs & PPOs*)	X	X		X	X
Face-to-face discussion with senior attending physician or senior resident to highlight potentially inappropriate PIMs and PPOs	X	X			
Face-to-face discussion with patient or nominated proxy (where patient does not have decision-making capacity) to explain details of recommended medication changes.		X			

OPTIMATE Trial

Principal Investigator: [name] [name]

Pre-discharge medication review, documentation of agreed medication adjustments and preparation of report for patient's GP with detailed explanation of recommended medication changes.		X			
Telephone contact with patient's GP to discuss medication changes.			X		
Telephone contact with patient or nominated proxy (where patient does not have decision-making capacity) to define current list of medications, discuss any medication issues and ascertain endpoint information.				X	X
Telephone contact with patient's pharmacist to define medication currently dispensed.			X	X (if necessary)	X (if necessary)

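### Participant blinding is not delivered and the blinded assessors are not identified, so readmission and ED attendance, taken first from patient or proxy report, can be captured differently by arm

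*Combined protocol and SAP*

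**What the plan says.** Blinding is described in three places.

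- Section 4.1 calls the trial a "prospective, single-blinded, randomized controlled multi-centre study" without naming the blinded party.
- Section 4.3 accepts that clinical staff know the intervention, but says that "the trial statistician and outcome assessors will remain blinded until the results are finalized".
- The schedule section (Study Procedures and Schedule of Events) gives the participant claim: "To mimic the intervention for blinding purposes of the participants, both control and intervention arm patients will receive a sham intervention", namely a modified adherence questionnaire (mMARS).

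On who knows the allocation, section 4.3 says that "primary researchers will receive randomization outcomes immediately upon activating the randomization request". Section 11.1 describes the primary researchers as the people who apply STOPP/START and the interaction software. An inclusion criterion in 4.2.1 reads "Agrees to primary researcher contacting the GP and community pharmacist post-discharge".

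On endpoint collection, Tables 1a and 1b both schedule a telephone call to the patient or a proxy/next of kin at 1 and 6 months, "to define current list of medications, discuss any medication issues and ascertain endpoint information". Both tables send the endpoint question to the GP only if patient or proxy cannot supply the answer. Registries are mentioned for mortality only.

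**The concern.** Blinding of participants and assessors matters most where the endpoint depends on what someone is asked and what they report. Here the patient or proxy is the first reporter of readmission and ED attendance, and the call that collects these events also covers medication. A patient who knows that their medicines were reviewed, or a caller who knows it, may recall, mention or probe for events differently from a control patient or caller.

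The primary endpoints in 6.1 and the cost per readmission and per ED attendance avoided in 6.3 rest on this ascertainment. EQ-5D-5L is self-assessed and more exposed; mortality is less so. The comparison of physician with pharmacist delivery is also less exposed, because both active arms follow Table 1a. The contrast at risk is each active arm against control.

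**Working it through.** **Step 1. Compare the two schedules.**

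| Item | Table 1a (intervention) | Table 1b (control) |
|---|---|---|
| Sham questionnaire (mMARS), baseline | yes | yes |
| Pre-discharge face-to-face explanation of medication changes to patient or proxy | yes | no |
| 1-week GP call about medication changes | yes | no |
| STOPP/START screening at 1 and 6 months | yes | no |
| Interaction screening at 1 and 6 months | yes | no |
| 1- and 6-month call combining medication and endpoints | yes | yes, nearly the same wording |
| GP asked about endpoints only if patient/proxy cannot say | yes | yes |
| Registries | mortality only | mortality only |

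The combined call is common to all arms, so the call alone is not the difference. What differs is what the patient has been told by then, and the screening attached to the same visits (the row "STOPP/START criteria (PIMs & PPOs" and the interaction row).

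**Step 2. Who could be blind?** Intervention patients or proxies have had recommended changes explained to them in person; a questionnaire common to all arms does not mask that. The primary researchers see the allocation (4.3), apply the screening (11.1) and contact GPs and pharmacists (4.2.1). No other caller is named, so they are the natural candidates for the patient call, but this is an inference.

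**Step 3. Reproduce the plan's sample size (4.3).** Inputs: 20% vs 12% (an 8-point reduction), two-sided 5%, 80% power. Unpooled formula: n = (1.960 + 0.842)² × (0.20×0.80 + 0.12×0.88) / 0.08² = 7.849 × 0.2656 / 0.0064 = 325.7, so 326. The pooled formula gives 329 and the arcsine formula 324.9. The stated 324 is reproduced within 3%. Then 3 × 324 = 972 and 972/0.7 = 1389. Power at 324 per arm (pooled z-test) is 79.5%.

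**Step 4. Illustrate differential capture.** The capture proportions and the 40% composite rate are assumptions; neither is in the documents. Let one arm record a fraction c of its events and the other all of them. With true risk p in both arms, the false difference is d = p(1 − c). The rejection probability is Φ((d − 1.96·SE₀)/SE₁) + Φ((−d − 1.96·SE₀)/SE₁), where SE₀ is the pooled and SE₁ the unpooled standard error at 324 per arm.

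*No true effect, active-arm capture lower:*

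| True rate p | c | False reduction | Two-sided rejection |
|---|---|---|---|
| 20% | 0.95 | 1 point | 6.2% |
| 20% | 0.90 | 2 points | 9.9% |
| 40% (assumed) | 0.95 | 2 points | 8.2% |
| 40% (assumed) | 0.90 | 4 points | 18.2% |

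At the 20% rate, the chance of a false significant benefit is 5.1% (c = 0.95) or 9.5% (c = 0.90), against a nominal 2.5% in that direction.

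*True 20% vs 12%, control capture lower:*

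| c in control | Observed control rate | Observed difference | Power |
|---|---|---|---|
| 1.00 | 20% | 8 points | 79.5% |
| 0.95 | 19% | 7 points | 69.3% |
| 0.90 | 18% | 6 points | 57.1% |

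**The case against.** The strongest reply is that no direct contradiction is shown for the assessors. The combined call is in both tables. No passage says that the primary researcher makes it; 4.2.1 names that person only for GP and pharmacist contact. Determination of readmission and of ED attendance are separate rows from the telephone call, which leaves room for a distinct blinded assessor. The Manual of Operations mentioned in 4.3 is not available here and may or may not settle the matter. All of this stands. A reader might infer that assessor blinding is plainly false; the documents support only that the assessors are unidentified and that no procedure for keeping them blind is given.

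A reader might also infer that every primary endpoint is biased and that this could never be checked. Neither follows. Admission and ED attendance are fairly objective events, the documents show a route for bias rather than bias itself, and hospital records would allow a check. No such check is planned.

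The figures are hypothetical, as objected. The 20% in 4.3 is also a medication-related readmission risk, whereas the aim in 2.2 is all-cause, so it serves only as a convenient base rate.

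The reply does not rescue participant blinding. The pre-discharge explanation is in Table 1a alone, and the people who receive it are the first reporters of the endpoint.

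**Conclusion.** The point holds in this form. Participant blinding is claimed but not delivered. Assessor blinding is claimed without saying who the assessors are. The stated order of sources, patient or proxy first and GP as fallback, leaves capture of readmission and ED attendance open to differences by arm. Direction and size are unknown.

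On the stated assumptions, a 5-10% relative shortfall in one arm creates a false difference of 1-2 points at a 20% rate (2-4 points at an assumed 40%), against a planned effect of 8. It raises two-sided rejection under no effect to 6.2-9.9% (8.2-18.2%). A shortfall in control instead lowers power from 79.5% to 69.3-57.1%. These figures show sensitivity and do not predict what will happen. The issue is worth correcting because correction is cheap; it does not by itself undermine the trial.

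**What to change.** 1. In all arms, make admission and ED records at the three participating hospitals the first source for readmission and ED attendance. Use patient/proxy and GP report for attendances elsewhere, in the same way in every arm. GPs of intervention patients may know the arm, so treat their reports as supplementary.
2. Have the records extracted by existing staff not involved with that patient, with the arm hidden in their eCRF view.
3. In the 1- and 6-month calls, ask and save the endpoint and EQ-5D-5L questions before any medication discussion, with one script for all arms.
4. In 4.1, 4.3 and the schedule section, state who is actually blinded (the statistician and the record extractor) and that participants and those delivering the intervention are not reliably blinded.

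The cost is a short endpoint procedure, an eCRF permission setting and some extra extraction time, plus a blinding statement that is weaker but true. It assumes that each site has a staff member not involved with the patient, which the documents do not confirm. Treatment, sample size and visit timing are unchanged.

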4.0 Study Procedures and Schedule of Events

The schedule of trial procedures for patient participants in the intervention arm of the trial are shown in Tables 1a and 1b below. To mimic the intervention for blinding purposes of the participants, both control and intervention arm patients will receive a sham intervention in the form of a modified version of the Medication Adherence Rating Scale (MARS; Thompson et al.).

Table 1a: Schedule of events for intervention patients

Timepoints	0/1	2	3	4	5
Study Visit	Baseline (within 72 hours of admission)	Pre-discharge (within 48 hours pre-discharge)	1 Week Follow-up (within 10 days post-discharge)	1 Month Follow-up (within 30 days post-discharge)	6 Month Follow-up (between 90 and 180 days post-discharge)
	Day 1	Day variable	Day 10 (+/- 3 days post-discharge)	Day 30 (+/- 7 days post-discharge)	Between Day 90 and Day 180 post-discharge
Inclusion / Exclusion criteria	X				
Decision-Making Capacity Functional Assessment	X	X**		X**	X**
Informed consent/ proxy assent	X	X**		X**	X**
Patient Demographics	X				
Medical History	X	X		X	X
Medication Reconciliation	X	X		X	X

OPTIMATE Trial

Principal Investigator: [name] [name]

FORTA* criteria	X	X		X	X
Laboratory Results	X	X			
Electrocardiogram review	X				
EQ5D-5L				X	X
Randomization	X				
Medication History (modified SHiM)	X				
Modified Medication Adherence Rating Scale (mMARS)	X				
Barthel Index Score	X	X			
Drug-drug interactions (Stockley's)	X	X		X	X
STOPP/START criteria (PIMs & PPOs*)	X	X		X	X
Face-to-face discussion with senior attending physician or senior resident to highlight potentially inappropriate PIMs and PPOs	X	X			
Face-to-face discussion with patient or nominated proxy (where patient does not have decision-making capacity) to explain details of recommended medication changes.		X			

OPTIMATE Trial

Principal Investigator: [name] [name]

Pre-discharge medication review, documentation of agreed medication adjustments and preparation of report for patient's GP with detailed explanation of recommended medication changes.		X			
Telephone contact with patient's GP to discuss medication changes.			X		
Telephone contact with patient or nominated proxy (where patient does not have decision-making capacity) to define current list of medications, discuss any medication issues and ascertain endpoint information.				X	X
Telephone contact with patient's pharmacist to define medication currently dispensed.			X	X (if necessary)	X (if necessary)
Telephone contact with patient's GP for endpoint ascertainment (if not available from patient or proxy).				X (if necessary)	X (if necessary)
Unscheduled Readmission Determination				X	X
Unscheduled Emergency Department Attendance Determination				X	X

Admission to residential care facility (long-term)				X	X
All-cause mortality check via registries or if necessary, with the patient's GP.				X	X

Table 1b: Schedule of events for control patients

Timepoints	1	2	3	4	5
Study Visit	Baseline (within 72 hours of admission)	Pre-discharge (within 48 hours pre-discharge)	1 Week Follow-up (within 10 days post-discharge)	1 Month Follow-up (within 30 days post-discharge)	6 Month Follow-up (between 90 and 180 days post-discharge)
	Day 1	Day variable	Day 10 (+/-3 days post-discharge)	Day 30 (+/- 7 days post-discharge)	Between Day 90 and Day 180 post-discharge
Inclusion / Exclusion criteria	X				
Decision-Making Capacity Functional Assessment	X	X**		X**	X**
Informed consent/ proxy assent	X	X **		X**	X**
Patient Demographics	X				
Medical History	X	X		X	X
Medication Reconciliation	X	X		X	X
FORTA* criteria	X	X		X	X

OPTIMATE Trial

Principal Investigator: [name] [name]

Laboratory Results	X	X			
Electrocardiogram review	X				
EQ5D-5L				X	X
Randomization	X				
Modified Medication Adherence rating Scale (mMARS)	X				
Barthel Index	X	X			
Telephone contact with patient or next-of-kin to define current list of medications, discuss any medication issues and ascertain endpoint information.				X	X
Telephone contact with patient's pharmacist to define medication dispensed.			X	X (if necessary)	X (if necessary)
Telephone contact with patient's GP for endpoint ascertainment (if not available from patient or proxy).				X (if necessary)	X (if necessary)
Unscheduled Readmission Determination				X	X
Unscheduled Emergency Department Attendance Determination				X	X

Admission to residential care facility (long-term)				X	X
All-cause Mortality check via registries or if necessary, with the patient's GP.				X	X

* PIMs – Potentially Inappropriate Medications; PPOs – Potentially inappropriate Prescribing Omissions; FORTA Fit fOR The Aged

** If necessary i.e. applies to participants who initially lacked decision-making capacity at the time of their enrolment.

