6.0 Outcome measures

6.1 Primary Outcome

- (i) unscheduled readmission within 30 days post-discharge,
- (ii) unscheduled readmission between 90 and 180 days post-discharge, and
- (iii) ED attendance within 30 and between 90 and 180 days post-discharge.

A primary composite endpoint of unscheduled readmission or ED attendance within 30 and between 90 and 180 days post-discharge will also be ascertained.

Treatment effects for each of the two intervention arms versus the control arm will be estimated for each outcome. Equivalence tests comparing the two active arms (for each outcome) will be done to compare DI delivery by physician with DI delivery by pharmacist.

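### The 1-month call that determines the 30-day primary endpoints has two conflicting windows, and both allow it before day 30 with no stated rule to recover later events

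*Combined protocol and SAP*

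**What the plan says.** Section 6.1 lists among the primary outcomes "unscheduled readmission within 30 days post-discharge" and "ED attendance within 30 and between 90 and 180 days post-discharge", together with a composite of the two over the same periods. Three primary results therefore have a risk period that closes on day 30.

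The Study Procedures and Schedule of Events section (the second section numbered 4.0) marks the determination of readmission and of ED attendance at two contacts only, 1 month and 6 months. In both Table 1a (intervention) and Table 1b (control) the 1-month contact is headed "1 Month Follow-up (within 30 days post-discharge" and, one line below, "Day 30 (+/- 7 days post-discharge". The 6-month contact is headed "6 Month Follow-up (between 90 and 180 days post-discharge".

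The source at each contact is a telephone call to the patient or a representative to "define current list of medications, discuss any medication issues and ascertain endpoint information". The back-up is "Telephone contact with patient's GP for endpoint ascertainment (if not available from patient or proxy". Registries are named for deaths only: "All-cause mortality check via registries or if necessary, with the patient's GP".

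Section 7.2 analyses binary outcomes by logistic regression. The section on tertiary endpoints says that the economic analysis will use every ED attendance and every unscheduled readmission of all randomized patients, but does not say how they will be collected.

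**The concern.** A window on both sides of day 30 suits a measure taken at a point in time, such as the EQ-5D-5L. It does not suit a cumulative count with a fixed closing day. A patient called on day 23 and readmitted on day 27 has a 30-day event, but the call that determines the endpoint came too soon to see it. Unless something later picks the event up and assigns it to the 30-day endpoint, the patient enters the logistic regression as a non-event with the same weight as a patient observed for the full 30 days.

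The two window lines also disagree with each other. One allows no call after day 30, and the other allows calls to day 37. A site cannot tell which governs, and the stricter reading pushes calls towards the side where events are lost.

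At stake are the event counts, the absolute risks and some of the precision of three primary results.

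**Working it through.** **The plan's own figure.** Section 4.3 gives 324 per group for 20% versus 12% at 180 days (two-sided 5%, 80% power). The usual two-proportion formula gives 329 with pooled variance and 326 with unpooled variance, and power at 324 is 79.5%. The inflation 972/(1 − 0.3) = 1388.6 rounds up to the stated 1389, or 463 per arm. The figure reproduces closely. It rests on 180-day risk, so this point does not affect it.

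**The windows.**
- Day line: 30 − 7 = 23 to 30 + 7 = 37. Calls on days 23 to 29 comply and leave up to 7 of 30 days (23%) unobserved.
- Heading line: any day up to 30. Every call before day 30 leaves part of the period unobserved.

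**Size of the loss (illustration).** Section 2.1 cites a 1-month readmission risk of 21.9% to 22.3%. I take R = 22% and assume a constant daily hazard.
- h = −ln(1 − 0.22)/30 = 0.00828 per day.
- Risk seen by a call on day d: F(d) = 1 − exp(−h·d).
- F(23) = 0.173, so 0.220 − 0.173 = 0.047 is missed. Unrounded, the share is 0.0466/0.22 = 21%, or about 15 events per 324 patients.
- Share missed, [R − F(d)]/R, for calls on days 23 to 29: 21.2%, 18.1%, 15.0%, 11.9%, 8.9%, 5.9%, 3.0%. The sum is 84.0%. From day 30 the share is zero.
- Calls spread evenly over the 15 days 23 to 37: 84.0/15 = 5.6% of events missed on average.
- Calls spread evenly over the 8 days 23 to 30: 84.0/8 = 10.5%.

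**Front-loaded hazard.** Use F(d) = 1 − exp[ln(0.78)·(d/30)^k]. For k = 0.5, F(23) = 0.196 and 11% is missed. For k = 0.7, F(23) = 0.186 and 15% is missed. Averaged evenly over days 23 to 37, the loss is about 3% and 4%.

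**Effect on the planned estimate.** Assume true 30-day risks of 22% and 14%, with the same share m of events missed in each arm. Power is two-sided 5%, normal approximation, 324 per arm.

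| m | Risks seen | Difference | Odds ratio | Power |
|---|---|---|---|---|
| 0 | 22.0% vs 14.0% | 8.0 points | 0.577 | 76% |
| 5.6% | 20.8% vs 13.2% | 7.6 points | 0.581 | 73% |
| 21.2% (every call on day 23) | 17.3% vs 11.0% | 6.3 points | 0.591 | 63% |

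The odds ratio hardly moves. The absolute difference and the power fall in step with the lost events.

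**The case against.** The strongest defence is that the events need not be lost. Both determinations are repeated at the 6-month contact, and neither row limits recall to days 90 to 180. The economic analysis is meant to use every ED attendance and unscheduled readmission, which presupposes capture of events between contacts. A full SAP is still to be pre-registered before database lock and could set derivation rules. Calls on days 30 to 37 also comply with the day line and cover the whole period.

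Much of this stands. It shows that complete capture is intended and that only patients called early are exposed. It does not close the gap. No text asks the 6-month call to look back to the interval between an early 1-month call and day 30, or says how such an event would be dated and assigned to the 30-day endpoint. The look-back would rest on recall at least two months after the event, and it fails for anyone lost in between, in a plan that allows for up to 30% attrition. A later SAP can define the derivation but cannot change when calls were made.

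A reader might also infer a bias between arms, because intervention patients have additional trial activity after discharge. The documents do not support that. The patient endpoint calls and their windows are the same in both tables, the 1-week pharmacist call is in both, and the extra 1-week contact for intervention patients is a GP call about medication changes.

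Nor do they support reading the window as inflating the 30-day risk with events from days 31 to 37. Section 6.1 limits the endpoint to 30 days, so such events are outside it by definition. What is missing is the event date needed to apply that limit.

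**Conclusion.** The point holds as a defect in ascertainment. Two stated windows for the same call contradict each other, both permit it before the risk period ends, and no stated rule recovers the remaining days. The consequence is under-counted 30-day events in all arms, a somewhat smaller absolute difference and some lost precision.

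If calls are spread evenly over days 23 to 37, the average loss is about 6% of events under constant hazard. It is about 10% if they are spread over days 23 to 30. It would be a mistake to take 21% as the expected loss: that figure needs a call on day 23 itself, and it falls to 11–15% if the hazard is front-loaded. These sizes rest on the cited background risk, an assumed hazard shape, an assumed spread of call dates and no recovery at 6 months. The documents give no actual call dates.

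It would also go too far to say that a site following the schedule necessarily produces false non-events, since some compliant calls observe the full 30 days.

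**What to change.** - In Tables 1a and 1b, replace the two lines for the 1-month contact with one endpoint-ascertainment window that opens on day 30, for example days 30 to 37.
- Record the date of every readmission and ED attendance on the eCRF, and count only events dated within 30 days of discharge towards the 30-day endpoints. State the rule in the SAP as well.
- For any patient contacted before day 30, have the 6-month contact ask explicitly about the interval from that call to day 30.

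The cost is a short amendment to two tables, one extra date field and slightly later calls for some patients. It is best done before further calls are made, because dates not collected at the time may not be recoverable.
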